- Screening serum creatinine or parathyroid hormone (PTH) levels ≥1.5 times the upper limit of normal is an exclusion criterion.
- All prior and concomitant medications and therapies must be collected from 30 days prior to study entry up until the final study visit. The protocol has inconsistent description of the process for the collection of Concomitant medications and therapies in Table 2, footnote 9 and Section 8.7.
- All pre-dose PK/PD/ADA samples during the Run-in Period and Main Study Period (Treatment Period) must be collected under fasting conditions, except for Day -7, -156 hour and Day -1, -12 hour samples. The post-dose PK/PD/ADA samples will not be collected under fasting conditions.
- Effective March 3rd, 2016, the Drug Safety Physician of this protocol is

Title: PPD Email: PPD

Phone number: PPD

If there are any questions concerning this change, please contact PPD by phone at PPD or by email at PPD This change will be captured in the next protocol amendment.

Sincerely.	PPD	
PPD		

Alexion Pharmaceuticals, Inc. [name]

Cc: eTMF, ISF
PPD Project Manager

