## 7. STATISTICAL ANALYSIS

For the statistical analyses below, descriptive statistics (n, mean, median, standard deviation [SD], 95% confidence interval [CI], minimum, and maximum) will be provided for each continuous variable, and frequencies and percentages will be provided for each categorical variable. Analyses will be conducted using Statistical Analysis Software (SAS©) version 9.2 or higher. Any hypothesis testing described will be 2-sided and performed at the 0.05 level of significance; p-values <0.05 will be considered statistically significant. In general, analyses will be presented by treatment cohort, and overall where specified. The 3 treatment cohorts are listed below:

Cohort #	Description	Label in output
Cohort 1:	Asfotase alfa 0.5 mg/kg initial single dose; followed by multiple dosing starting after 2 weeks at 0.5 mg/kg 3 times per week	0.5 mg/kg cohort
Cohort 2:	Asfotase alfa 2.0 mg/kg initial single dose; followed by multiple dosing starting after 2 weeks at 2.0 mg/kg 3 times per week	2.0 mg/kg cohort
Cohort 3:	Asfotase alfa 3.0 mg/kg initial single dose; followed by multiple dosing starting after 2 weeks at 3.0 mg/kg 3 times per week	3.0 mg/kg cohort

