#### 7.2.2. Secondary Endpoint

For the secondary endpoint, PLP change from Baseline to pre-3rd dose Week 9, similar methods as for PPi will be employed in the FA Set and PP Set.

Sensitivity analyses for PLP may be employed for any patients without taking any vitamin B6 or with consistent input of vitamin B6, defined as taking same dose of vitamin B6 during the study. Vitamin B6 usage will be obtained from the concomitant medications.

Additionally for sensitivity, the within-patient mean absolute levels of the pre-treatment "fasting" PLP samples (-168 h, -24 h, pre-dose Day 1) and the "non-fasting" PLP samples (-156 h, -12 h) will be compared using the exact Wilcoxon rank-sum test for all patients in the FA Set. If a statistical difference is detected between the pre-treatment "fasting" and "non-fasting" samples, given samples on treatment are collected under both "fasting" and "non-fasting"

conditions, the change to each post-treatment timepoint will be evaluated descriptively using the matched "fasting" or "non-fasting" average at Baseline; accordingly, "fasting" post-treatment samples will use a "fasting" Baseline and "non-fasting" post-treatment samples will use a "non-fasting" Baseline.

Please refer to Table 4 on how to handle the values fall under the lower limit of quantification (LLOQ).

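### SAP 7.2.2 shows the matched fasting/non-fasting PLP Baseline only after a significant pre-test that can easily miss a moderate fasting difference; the matched result should always be shown

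*SAP*

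**What the plan says.** SAP section 5.1.2 defines PLP Baseline as the average of all available pre-dose samples: -168 h, -156 h, -24 h, -12 h and pre-dose Day 1. The derived-variable rules in SAP section 9.3 repeat this. Under Administrative Change Letter #2, pre-dose samples are fasting except those at -156 h and -12 h. For samples after dosing the letter says: "The post-dose PK/PD/ADA samples will not be collected under fasting conditions". A complete Baseline therefore mixes three fasting and two non-fasting samples, while every later sample is one or the other.

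SAP section 7.2.2 addresses this as a sensitivity matter: "Additionally for sensitivity, the within-patient mean absolute levels of the pre-treatment 'fasting' PLP samples" and their non-fasting counterparts "will be compared using the exact Wilcoxon rank-sum test for all patients in the FA Set". The next step is conditional: "If a statistical difference is detected between the pre-treatment 'fasting' and 'non-fasting' samples, given samples on treatment are collected under both 'fasting' and 'non-fasting". Only then does the matched analysis follow, in which "the change to each post-treatment timepoint will be evaluated descriptively using the matched" Baseline for that fasting state. SAP section 7 sets the threshold: "Any hypothesis testing described will be 2-sided and performed at the 0.05 level of significance; p-values <0.05 will be considered statistically significant". Nothing is planned for a non-significant result, and neither an estimate nor a confidence interval for the fasting difference is requested.

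**The concern.** A significance test decides whether readers see the only planned analysis that matches fasting state. When that test has little chance of detecting a moderate difference, the matched tables will often be missing when they would be informative.

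The outputs at stake are those that read PLP change within a cohort: descriptive change at each timepoint, signed-rank tests against zero, model-estimated change by visit, and the time profile. These apply to PLP because SAP section 7.2.2 adopts methods similar to those for PPi. In the profile, fasting pre-dose and non-fasting 6 h post-dose samples alternate. A fasting difference would then appear as a swing around each dose and could be read as a drug effect.

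**Working it through.** **Stated power.** The documents give no power for the PLP pre-test. Their power statements (protocol 11.5.8, SAP 9.2) concern the PPi cohort comparison. Those reproduce per comparison by two-sample t-test: 86.3% for 9 per cohort and 2.3 µM, and 91.4% for 6 per cohort and 3.2 µM, both with SD 1.5 µM. They do not bear on the pre-test.

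**Inputs.**
- From the documents: 3 fasting and 2 non-fasting Baseline samples (SAP 7.2.2, Letter #2); two-sided 0.05 (SAP 7); 27 patients randomized (SAP 9.2); unpaired exact rank-sum test (SAP 7.2.2).
- Assumed, because the documents give no figure: the size of the fasting difference, the SD of PLP, and the correlation between a patient's fasting and non-fasting means. Data are taken as normal.

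**Step 1: offset from the pooled Baseline.** Let F be a patient's fasting pre-treatment mean and F + d the non-fasting mean.
- Pooled Baseline = [3F + 2(F + d)] / 5 = F + 0.4d.
- At a fasting timepoint with value Y, the change is Y - F - 0.4d, an offset of -0.4d. This includes pre-3rd dose Week 9.
- At a non-fasting timepoint, if the same d persists on treatment, the change is (Y + d) - (F + 0.4d) = (Y - F) + 0.6d, an offset of +0.6d.
- The gap between the two kinds of timepoint is 0.6d - (-0.4d) = d.
- With matched baselines both offsets are 0, on the same assumption.
- If Baseline samples are missing, the fasting-timepoint offset can range from 0 (only fasting samples available) to -1.0d (only non-fasting).

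For example, d = 0.5 SD gives -0.4 × 0.5 = -0.2 SD at fasting timepoints and +0.6 × 0.5 = +0.3 SD at non-fasting ones.

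**Step 2: comparison between cohorts.** With similarly complete Baseline sampling, each randomized cohort has expected offset -0.4d at pre-3rd dose Week 9. The difference is -0.4d - (-0.4d) = 0.

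**Step 3: how often the pre-test misses d.** Fasting and non-fasting patient means were simulated as bivariate normal with unit SD, n = 27, 4,000 trials per setting. The miss rate is the share of trials with p ≥ 0.05.

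| Correlation | 0.5 SD: rank-sum (planned) | 0.5 SD: signed-rank (paired) | 0.3 SD: rank-sum | 0.3 SD: signed-rank |
|---|---|---|---|---|
| 0 | 59% | 60% | 81% | 81% |
| 0.5 | 61% | 32% | 90% | 70% |
| 0.7 | 64% | 12% | 93% | 54% |
| 0.8 | 63% | 3% | 95% | 36% |
| 0.9 | 63% | 0% | 98% | 10% |

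Repeat runs agree to within about a point or so, which is why the range for 0.5 SD is given as 58% to 64%. At 0.25 SD the rank-sum test misses about 86% to 99% over the same correlations. The signed-rank test misses about 51% at correlation 0.8.

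**Step 4: why the planned test does so poorly.** The two means come from the same patients, but the rank-sum test treats them as independent groups. The variance of the paired difference is 2(1 - correlation) in these units, while the test in effect assumes 2. With no fasting effect it rejects about 5% of the time at correlation 0, 0.5% at 0.5, and essentially never from 0.7 upward. A paired test removes much of the problem for consistent shifts of 0.5 SD, but not for smaller ones unless the correlation is high.

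**The case against.** The strongest reply is that little depends on this trigger. The matched evaluation is labelled a sensitivity analysis and is descriptive, so no test or decision rests on it. That stands, and it limits how serious the point can be.

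Several stronger readings are tempting, and the documents do not support them.
- *The SAP takes non-significance as proof of no fasting effect.* It draws no such conclusion. It states only when an extra analysis is produced.
- *The pre-test causes a biased Baseline to be kept for the secondary endpoint.* The pooled average is the defined Baseline whatever the pre-test shows, and no text replaces it after a significant result. Bias also presupposes a real fasting difference, whose size is not given.
- *The between-cohort PLP comparison is compromised.* A common additive offset largely cancels under randomization (Step 2).
- *Power should be judged at 18 patients.* That is the minimum number of completers. The pre-test uses pre-treatment samples from the FA Set, which needs one dose and one pre-treatment and one on-treatment PPi result. Later dropouts stay in, so the number should be close to 27.
- *The test fails a required power level.* None is set for it.

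Two further objections stand. The difference d is not a pure fasting effect: each non-fasting Baseline sample is drawn 12 h after a fasting one, so time of day is mixed in. Post-dose samples at 24, 48 and 72 h also count as non-fasting under Letter #2, though they fall at a different clock time from the non-fasting Baseline samples. In addition, the +0.6d offset requires d to persist while treatment is meant to change PLP. The matched Baseline is therefore an informative alternative, not a definitive correction.

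The plan also provides absolute levels, individual curves and an optional vitamin B6 sensitivity analysis. These help a careful reader, but none matches change from Baseline to fasting state.

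**Conclusion.** The point holds as a minor improvement to a sensitivity analysis. The only planned analysis that matches PLP change to fasting state depends on a pre-test with a high chance of missing a moderate difference: about 58% to 64% at 0.5 SD and 86% to 99% at 0.25 SD, for 27 patients and correlations from 0 to 0.9. Much of that loss comes from using an unpaired test on paired data. A signed-rank test would miss about 12% at 0.5 SD and correlation 0.7, but still about half at 0.25 SD and correlation 0.8. Changing the test alone therefore does not settle the matter.

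When the difference is missed, within-cohort changes carry -0.4d at fasting timepoints and, if d persists, +0.6d at non-fasting ones, with no matched result beside them. The -0.4d follows from the sampling schedule with complete Baseline data. The miss rates rest on assumed normal data, effect sizes and correlations. Whether d is large enough to matter cannot be judged from the documents, which is a reason to estimate it.

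**What to change.** In SAP section 7.2.2:
1. Delete the condition that a statistical difference be detected.
2. Always present the matched-baseline PLP change beside the pooled-baseline result, as a descriptive sensitivity analysis: fasting samples against the mean of -168 h, -24 h and pre-dose Day 1, and non-fasting samples against the mean of -156 h and -12 h.
3. Replace the rank-sum pre-test with the within-patient fasting minus non-fasting difference and its paired 95% CI, reported as an estimate and not used as a trigger.
4. State that fasting state is confounded with sampling time, so neither the difference nor the matched result isolates fasting.

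The pooled Baseline stays the main analysis. The cost is SAP wording and one set of tables that is already specified conditionally; no new data are needed. The downside is that matched baselines average three or two samples instead of five and are somewhat noisier, which is why both results should be shown.

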#### 7.2.3. Tertiary Analyses

Not Applicable.

#### 7.2.4. Other Efficacy Analyses

Not Applicable.

#### 7.2.5. Pharmacokinetic and Pharmacodynamic Analyses

Pharamcokinetic analyses and analyses relating PK and PD will be described in a separate analysis plan.

### 7.3. Safety Analyses

All safety analyses will be conducted on the Safety Set based on the treatment actually received. All safety data will be summarized in tabular format by treatment cohort and overall, and all data will be in by-patient data listings. See Appendix 9.3 for the definition of Treatment Baseline for Safety analyses. No formal hypothesis testing is planned. Missing or invalid safety data will not be replaced.

#### 7.3.1. Study Duration, Treatment Compliance, and Exposure

Study duration, treatment compliance, and exposure will be summarized for the Safety Set by treatment cohort, according to the treatment actually received.

Study duration is defined as the time from first dose to the end of the main study period (ie, Week 13: Day 87) or study discontinuation date, whichever occurs first. The period after Day 87 up to the Safety Follow-up call at 90 days after last dose will not be included in the calculation.

Study treatment compliance will be defined as the percentage of reported injections taken out of the total number of expected reported injections from the dosing diaries up to the point of study completion or discontinuation. If a patient discontinues prematurely from the study, his or her compliance will be based on the period up to the point of discontinuation from the study. A separate study treatment compliance analysis will be conducted counting only reported injections where the milligram administered complies within a 10% window of the expected dose based on the weight linked to the dosing event.

Study drug administration data will be presented by treatment cohort in a listing. The date/time of first injection, end time of last injection (if multiple), injection location(s), total volume administered (mL), and number of injections will be included. In addition, tabular summaries will be produced by treatment cohort for the average daily dose (mg/kg) including all expected

dosing events on study and average weekly dose (mg/kg/week) during the multiple Dosing Period, derived from the volume administered and weight linked to each dosing event.

#### 7.3.2. Adverse Events (AEs)

Adverse events will be coded in MedDRA and presented by SOC and PT. Adverse events occurring on or after first treatment, treatment-emergent AEs (TEAEs), will be tabulated and presented by treatment cohort and overall. Summaries for pre-treatment AEs (PTAEs) will be included only where appropriate and specified. See Appendix 9.3 of the SAP for further details on the difference between TEAEs and PTAEs. Study displays to be included are described below.

#### 7.3.2.1. Overall Summary of Adverse Events

An overall summary of the following categories of AEs will be presented by treatment cohort and overall, including summaries of events (n) and number of patients with events (n, %): TEAEs, treatment-emergent SAEs, and treatment-emergent non-SAEs. Within each category, the following subcategories will also be summarized:

- Mild/Moderate/Severe TEAEs
- Related TEAEs (possibly, probably, definitely related, or missing relationship)
- TEAEs leading to withdrawal from the study
- TEAEs leading to death
- AESI, see Section 7.3.2.7

A summary of events (n) and number of patients with events (n, %) for PTAEs will also be included with the following subcategories: Mild/Moderate/Severe AEs, AEs leading to withdrawal, and AEs leading to death (note that Related AEs and AESI do not apply to PTAEs).

A listing of all TEAEs by treatment cohort and patient will be presented. Separate listings will be produced for treatment-emergent SAEs, AEs leading to study drug withdrawal, AEs resulting in death, and PTAEs.

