#### 6.3. Safety Set

All patients who received at least one dose of study drug will be included in the Safety Set. Patients will be considered, for safety analysis, to be in the treatment cohort of the treatment they actually received.

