#### 7.1. Study Patients

#### 7.1.1. Disposition of Patients

The number and percent of patients completing the study will be described. For patients who discontinued the study, the reason for discontinuation will be summarized. In addition, the number of patients who discontinued study drug permanently due to an AE will be summarized. Information will be reported using all randomized patients and summary statistics will be presented by treatment cohort and overall.

A listing of patients indicating randomization to treatment, attendance at each visit (home or inclinic), discontinuation from the study, and completion of the study will also be generated.

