#### 7.3.2.2. AEs by SOC and PT

The number of TEAEs and the number and percentage of patients with events will be presented by SOC and PT. Patients are counted once in each SOC and PT. Percentages will be based on the total number of treated patients in the treatment cohort. Treatment-emergent SAEs, treatmentemergent non-SAEs, and PTAEs will be summarized using the same approach.

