#### **Adverse Events**

Additional details for the analysis of Adverse Events described in Section 7.3.2:

Treatment-emergent AEs (TEAEs) are events with start dates and start times on or after the date and time of the first study drug dose. If the start date of an AE is partially or completely missing and the end (stop) date and time of the AE does not indicate that it occurred prior to first dose, then the determination of treatment-emergent status will be based on the following:

If the start year is after the year of the first study drug dose, then the AE is treatment-emergent; else,

If the start year is the same as the year of the first study drug dose and the start month is missing, then the AE is treatment emergent; else if the start month is present and is the same or after the month of the first study drug dose, then the AE is treatment-emergent; else, if the start date is completely missing, then the AE is treatment-emergent.

Pre-Treatment Adverse Events (PTAEs) are the AEs occur after the time of informed consent up through the Run-In Period and prior to the 1st dose.

Patient percentages are based on the total number of treated patients in the particular treatment cohort.

Related AEs are defined as possible, probable or definitely related, or events with missing relationship status. Unrelated AEs are defined as unlikely or not related.

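### Pre-treatment AE tables are restricted to dosed patients, so their withdrawal and death rows cannot count anyone whose event ended participation before Day 1 (minor)

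*SAP*

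**What the plan says.** SAP 9.3 (Adverse Events) sets the window: "Pre-Treatment Adverse Events (PTAEs) are the AEs occur after the time of informed consent up through the Run-In Period", and in any case before the first dose. The same appendix separates pre-treatment from treatment-emergent events by when the event started.

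SAP 7.3.2.1 asks for an overall PTAE summary: "A summary of events (n) and number of patients with events (n, %) for PTAEs will also be included with the following subcategories". The rows are these: "Mild/Moderate/Severe AEs, AEs leading to withdrawal, and AEs leading to death (note that Related AEs and AESI do not apply to PTAEs". SAP 7.3.2.2 then has PTAEs tabulated by System Organ Class and Preferred Term in the same way as treatment-emergent events, where "Percentages will be based on the total number of treated patients in the treatment cohort". SAP 9.3 repeats the treated-patient denominator.

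The population is fixed one level up. SAP 7.3 states that "All safety analyses will be conducted on the Safety Set based on the treatment actually received", and SAP 6.3 defines that set: "All patients who received at least one dose of study drug will be included in the Safety Set". No section of the SAP names another population for PTAEs.

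For disposition the SAP chooses differently. In SAP 7.1.1, "Information will be reported using all randomized patients", with reasons for discontinuation, by cohort and overall.

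**The concern.** The table is built to show, among other things, pre-treatment events that led to withdrawal or death. The most direct case is a patient who consents, has an event during screening or run-in, and leaves or dies before Day 1. That patient is never dosed and so never enters the Safety Set. The population rule removes the very patients those two rows would be expected to capture.

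What is at stake is how the report is read. A zero in either row would naturally be taken to mean that no pre-dose event caused a withdrawal or death, and the table cannot support that statement. In an open-label study that assigns cohort before dosing, a reader may want to know whether AEs caused losses between randomisation and first dose.

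**Working it through.** No figure in the plan is in dispute. The check sets the definitions side by side.

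**Inputs**

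| Item | Rule | Source |
|---|---|---|
| AE collection | Starts when consent is signed | Protocol 9.4.1.4 |
| Pre-dose period | Screening Week -12 to Week -2, then run-in at Week -1 | Protocol 6.2 |
| Randomisation | During run-in, before the first dose | Protocol 8.3 |
| PTAE window | After consent, before first dose | SAP 9.3 |
| Population | Safety Set, at least one dose | SAP 7.3, 6.3 |
| Denominator | Treated patients in the cohort | SAP 7.3.2.2, 9.3 |
| Planned numbers | 36 screened, 27 randomised | Protocol synopsis |

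**Who can be counted in the withdrawal and death rows**

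1. *PTAE during screening, patient leaves or dies before randomisation.* Not dosed, so not in the Safety Set. Counted: no.
2. *PTAE, patient randomised, leaves or dies before Day 1.* Not dosed, so not in the Safety Set. There is also no treatment actually received by which to choose a cohort column. Counted: no.
3. *PTAE begins before dosing, patient is dosed, and the same event later leads to withdrawal or death.* In the Safety Set, and the event is still a PTAE because its start time decides. Counted: yes.

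Only the third kind can fill the rows. The rows are not zero by definition, but every withdrawal or death that took place before dosing contributes 0.

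**Size**

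On the planned numbers, 36 − 27 = 9 screened patients are never randomised, and 9/36 = 25% of those screened lie outside the Safety Set for that reason. Anyone randomised but not dosed is added to them. This counts people, not events. The documents say nothing about how many of them might have an AE.

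Purely as an assumed range, if 1, 2 or 3 of the 27 randomised patients left before dosing because of an AE, the proportions of those randomised would be 1/27 = 3.7%, 2/27 = 7.4% and 3/27 = 11.1%. In each case these patients would add nothing to the row. The plan gives no basis for preferring any of these values.

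**The case against.** The strongest reply is that the information is mostly available elsewhere. The disposition table covers all randomised patients and gives the reason for discontinuation by cohort, so a randomised patient who left before dosing because of an AE would appear there. Protocol 11.5.6.1 also promises an AE listing for all patients and a separate listing of patients withdrawing because of AEs. These events precede any drug exposure, the SAP itself says relatedness does not apply to them, and no formal testing of safety data is planned.

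Much of this stands, and it is why the point is minor. It does not close the gap:

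- Disposition gives no severity, System Organ Class or Preferred Term, and does not reach consented patients who were never randomised.
- The SAP's own PTAE and death listings fall under the Safety Set rule of 7.3. Its withdrawal listing concerns withdrawal of study drug, which an undosed patient cannot have.
- The protocol's all-patient listing helps on its plain wording, although Protocol 11.5 also places safety analyses on the Safety Set.

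A reader might go further and infer that the report would contradict itself, with disposition showing a pre-dose AE withdrawal where the PTAE table shows none. The documents do not support that. The two tables have different stated populations, and different counts on different populations are not a contradiction. Nor are the rows mislabelled: an event that starts before dosing and later causes withdrawal is, under SAP 9.3, a PTAE leading to withdrawal. The rows are incomplete, not wrong.

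**Conclusion.** The point holds as a minor defect in safety reporting. A stated rule, not a missing detail, excludes from the PTAE tables every patient whose event ended participation before Day 1. The withdrawal and death rows therefore cover only part of what a reader would take from them.

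The loss cannot be sized. A reader might take the 25% of screened patients who are never randomised as the share of events lost. It is only the planned gap between screening and randomisation, and nothing in the documents says that any of those patients had an AE. The assumed 1 to 3 of 27 is an illustration, not an expectation, and the interval between randomisation and dosing is at most about a week.

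The conclusion assumes that SAP 7.3 is applied as written to the PTAE tables. The primary endpoint, the cohort comparisons and the treatment-emergent AE tables are not affected.

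**What to change.** In SAP 7.3, 7.3.2.1, 7.3.2.2 and the denominator rule in 9.3, exempt PTAEs from the Safety Set rule and state their own population:

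- an overall column on all consented patients, with the number consented as denominator;
- cohort columns on all randomised patients, by randomised cohort, with the number randomised as denominator;
- the PTAE listing on all consented patients;
- a footnote explaining that the overall and cohort columns have different denominators, and that both differ from the treatment-emergent tables.

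The overall column needs all consented patients. A table on randomised patients alone would still omit withdrawals and deaths during screening, which is most of the PTAE window. Treatment-emergent tables stay on the Safety Set.

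The cost is SAP wording, a population flag and a footnote. No new data are needed, because AEs are collected from consent. The downside is a denominator that differs from the treatment-emergent tables. If the sponsor prefers to keep the present population, labelling the PTAE rows as dosed patients only would prevent the misreading, but would not recover the missing counts.
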